9.3.3 Missing Post-baseline Evaluation in Open-label Treatment Phase

Primary analysis of efficacy endpoints will be conducted on observed data without imputation.

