8. WITHDRAWAL FROM TREATMENT, PROCEDURES, AND STUDY

8.1 Subjects' Decision to Withdraw

Subjects have the right to withdraw from the study at any time and for any reason without prejudice to their future medical care by the physician or at the institution.

Subjects can decline to continue receiving investigational product and/or other protocol-required therapies or procedures at any time during the study but continue participation in the study. If this occurs, the investigator is to discuss with the subject the appropriate processes for discontinuation from investigational product or other protocol-required therapies and must discuss with the subject the options for continuation of the Schedule of Assessments ([Table 1](#)) and collection of data, including endpoints and adverse events. The investigator must document the change to the Schedule of Assessments ([Table 1](#)) and the level of follow-up that is agreed to by the subject (eg, in person, by telephone/mail, through family/friends, in correspondence/communication with other physicians, from review of the medical records).

Withdrawal of consent for a study means that the subject does not wish to receive further protocol-required therapies or procedures, and the subject does not wish to or is unable to continue further study participation. Subject data up to withdrawal of consent will be included in the analysis of the study, and where permitted, publicly available data can be included after withdrawal of consent. The investigator is to discuss with the subject appropriate procedures for withdrawal from the study.

8.2 Investigator or Sponsor Decision to Withdraw or Terminate Subjects' Participation Prior to Study Completion

The investigator and/or sponsor can decide to withdraw a subject(s) from investigational product and/or other protocol-required therapies, protocol procedures, or the study as a whole at any time prior to study completion.

Subjects may be eligible for continued treatment with Amgen investigational product(s) and/or other protocol-required therapies by a separate protocol or as provided for by the local country's regulatory mechanism, based on parameters consistent with [Section 12.1](#).

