8.3 Reasons for Removal From Treatment and Study

8.3.1 Reasons for Removal From Treatment

Reasons for removal from protocol-required investigational product(s) or procedural assessments include any of the following:

- Subject request
- Safety concern (eg, due to an adverse event, failure to follow contraception, breast feeding, requirement for treatment not allowed in the protocol, and/or protocol requirements)
- Death
- Lost to follow-up
- Decision by sponsor (other than subject request, safety concern, lost to follow-up)
- Lack of efficacy

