8.3.2 Reasons for Removal From Study

Reasons for removal of a subject from the study are:

- Decision by sponsor
- Withdrawal of consent from study
- Death
- Lost to follow-up

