Number of headache days in **between each monthly IP dose intervals and normalized to 28 day equivalent** relative to study day 1 in the first 3 months, or between the month 5 and 6 visit, or between the month 9 and 10 visit, **or between the month 12 and 13 visit. Days without eDiary data are handled by proration according to [Section 9.3](#).**

Migraine Attack

An episode of any qualified migraine headache or episode for which the subject took a triptan or ergot-derivative to treat headache or aura. The following rules will be used for distinguishing an attack

of long duration from two attacks or for distinguishing between attacks and relapses:

- a) A migraine attack that is interrupted by sleep, or temporarily remits, and then recurs within 48 hours after onset of the attack will be considered as one attack and not two.
- b) An attack primarily treated successfully with medication but with relapse within 48 hours **of onset of attack** will be considered as one attack.
- c) **A migraine attack lasting more than 48 hours will be counted as one attack.**

Monthly Migraine Attacks

Number of migraine attacks **between each monthly IP dose and normalized to 28 day equivalent** relative to study day 1 in the first 3 months, or between the month 5 and 6 visit, or between the month 9 and 10 visit or **between the month 12 and 13 visit**. **Days without eDiary data are handled by proration according to [Section 9.3](#)**. For the definition of a migraine attacks, see above.

Fifty Percent Responder Rate

At least 50% reduction from baseline in monthly migraine days. **Percentage change from baseline in monthly migraine days is used to determine 50% responder (see [Section 6.6](#))**.

Monthly Cumulative Hours of Migraine Headache

Cumulative duration of any qualifying migraine headache which occurs during each migraine day **between each monthly IP dose and normalized to 28 day equivalent** relative to study day 1 in the first 3 months, or between the month 5 and 6 visit, or between the month 9 and 10 visit, or **between the month 12 and 13 visit**, regardless of acute treatment use. **Days without eDiary data are handled by proration according to [Section 9.3](#)**.

Monthly Acute Medication Use in Days

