40	Week 36 dose date; study day 253 if week 36 dose is not received (either missed or IP discontinued prior to week 36)	Week 40 IP dose date-1; study day 280 if week 40 dose is not received (either missed or IP discontinued prior to week 40)
44	Week 40 dose date; study day 281 if week 40 dose is not received (either missed or IP discontinued prior to week 40)	Week 44 IP dose date-1; study day 308 if week 44 dose is not received (either missed or IP discontinued prior to week 44)
48	Week 44 dose date; study day 309 if week 44 dose is not received (either missed or IP discontinued prior to week 44)	Week 48 IP dose date-1; study day 336 if week 48 dose is not received (either missed or IP discontinued prior to week 48)
52	Week 48 dose date; study day 337 if week 48 dose is not received (either missed or IP discontinued prior to week 48)	Study day 364

Note: for the intervals in month 6, 10, and 13 all available data before the next planned IP dose or visit should be used for calculation. Also refer to the definition of Monthly Migraine Days in [Section 6.1.2](#).

Study Visit

Since the actual visit for a subject may not exactly coincide with his/her targeted visit date, the actual visit date is mapped to the study visit as follows (visit windows below only apply to visits other than safety follow-up visit):

Study Phase	Study Visit	Target Day	Study Day
Open-label Treatment Phase	Day 1	1	1
	Week 4	29	2-43
n = 2 to 13	Week 4n	28n+1	28n-12 to 28n+15
	Week 8	57	44-71
	Week 12	85	72-99
	Week 16	113	100-127
	Week 20	141	128-155
	Week 24	169	156-183
	Week 28	197	184-211
	Week 32	225	212-239
	Week 36	253	240-267
	Week 40	281	268-295
	Week 44	309	296-323
	Week 48	337	324-351
	Week 52	365	352-379
	Safety Follow-up	The nominal visit from RAVE	

Note: If more than one visit (including the unscheduled visits, ie, CPEVENT='UNSCHED') fall within the same defined window, **scheduled visit will be used regardless of the distance from the target day. Unscheduled visit will only be used when there is no scheduled visit in the defined window.** The closest visit to the target day **among the same type of visit (scheduled vs. unscheduled)** will be considered for analysis. If two assessment dates are equidistant from the target date, the latter visit will be considered for analysis.

Above study visit table will be used for lab, vital signs, C-SSRS and PROs collected during office visit.

For adverse event, analysis windows will be set up based on study phase:

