7.2 Efficacy Analysis Set

The Efficacy Analysis Set (EAS) includes subjects who were enrolled and received at least one dose of IP and **had at least one change from baseline measurement in monthly migraine day** in study 20130255. **Subjects will be analyzed according to their randomized treatment group in the parent study 20120295 and the first dose received in the 20130255 OLE study, irrespective if a subject received only AMG 334 70 mg, 140 mg or both 70 mg and 140 mg in the 20130255 OLE study.**

Treatment group identifiers will be as follows:

- **Placebo / AMG 334 70 mg**
- **Placebo / AMG 334 140 mg**
- **AMG 334 70 mg / 70 mg**
- **AMG 334 70 mg / 140 mg**
- **AMG 334 140 mg / 70 mg**
- **AMG 334 140 mg / 140 mg**

Analyses for efficacy endpoints and patient reported outcomes (PROs) will utilize this analysis set except C-SSRS and MPFID.

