10.5 Efficacy Analyses

The analysis for efficacy endpoints will utilize the efficacy analysis set. Subjects will be analyzed according to their randomized treatment groups in the parent study 20120295 **and the first dose received in the 20130255 OLE study.**

For primary analysis of efficacy endpoints summary statistics on observed data are provided by visit and treatment group. Subgroup analysis of the secondary efficacy endpoints on observed data will be provided by sex, race, region and medication overuse, and by visit and treatment group.

PROs include PROMIS Pain interference, migraine symptom interference items, MSQ, **MPFID** and MIDAS. Change from baseline in total score (or subscale if applicable) of each PRO will be summarized descriptively on observed data by visit and treatment group. No sensitivity analysis will be conducted for PROs.

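### The 50% responder rate through month 13 is reported on observed cases only, with no pre-specified missing-data sensitivity analysis, so late-visit rates may be biased upward

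*SAP*

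**What the plan says.** - **Analysis rule.** SAP 9.3.3: "Primary analysis of efficacy endpoints will be conducted on observed data without imputation". SAP 10.5 repeats it: "For primary analysis of efficacy endpoints summary statistics on observed data are provided by visit and treatment group".
- **Responder definition.** SAP 6.1.2: "At least 50% reduction from baseline in monthly migraine days". No rule there or in SAP 6.6 counts a missing month as non-response.
- **When a month is missing.** Under SAP 9.3, a monthly interval with fewer than 14 diary days is set to missing; otherwise counts are prorated to 28 days. For missing intervals 9.3 points to 9.3.2, which deals with missing baseline; the post-baseline rule is in 9.3.3.
- **Analysis set.** The SAP 7.2 efficacy set is limited to dosed subjects who "had at least one change from baseline measurement in monthly migraine day". They are grouped by parent-study arm (placebo, 70 mg, 140 mg) and first open-label dose (70 mg or 140 mg), giving six groups. Protocol 10.4.1 assigns efficacy to the full analysis set, while protocol 10.4.2 names an efficacy analysis set that protocol 10.1.2 does not define.
- **Stopping treatment and leaving the study.** Protocol 8.3.1 lists "Lack of efficacy" among the reasons for removal from treatment. Protocol 8.3.2, which begins "Reasons for removal of a subject from the study are", gives sponsor decision, withdrawal of consent, death and loss to follow-up, and not lack of efficacy. Protocol 8.1: "Subjects can decline to continue receiving investigational product" and still continue in the study.
- **Attrition reporting.** SAP 9.4 names the timing of and reasons for early withdrawal as a possible source of bias, plans to tabulate or list them, and allows an ad hoc time-to-withdrawal analysis. SAP 10.2 gives disposition, with reasons for withdrawal from the product, by open-label entry dose.

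**The concern.** The secondary objective is to characterise long-term efficacy, and the responder proportion is one of its four measures. With an observed-case percentage the denominator can shrink from visit to visit. If the subjects who disappear are mostly those who were not responding, the percentage rises although nobody has improved. A reader of a table running from month 1 to month 13 could take that rise as a gain or as sustained benefit.

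The plan recognises withdrawal as a possible source of bias but does not carry that through to an efficacy analysis. SAP 9.3 uses the term sensitivity analysis without defining one for missing efficacy data, SAP 10.5 rules it out for patient-reported outcomes, and SAP 9.5 mentions only ad hoc work on extreme values.

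**Working it through.** **Inputs from the documents.** Up to 651 subjects may participate (protocol 10.2, SAP 3.2). Diary months are 1, 2, 3, 6, 10 and 13 (SAP 6.1.2). The documents state no dropout rate, responder rate or precision target for efficacy, so there is no planned figure to reproduce.

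**Assumed inputs.** Observed responder rate p = 50%; missing fraction d = 10%, 20% or 30%; responder rate q among the missing = p, p/2 or 0.

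**Formula.** All-subject rate = (1 − d)p + dq. Observed rate minus all-subject rate = d(p − q).

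| d | q = p | q = p/2 | q = 0 |
|---|---|---|---|
| 10% | 50% | 0.9 × 50 + 0.1 × 25 = 47.5% | 0.9 × 50 = 45% |
| 20% | 50% | 0.8 × 50 + 0.2 × 25 = 45% | 0.8 × 50 = 40% |
| 30% | 50% | 0.7 × 50 + 0.3 × 25 = 42.5% | 0.7 × 50 = 35% |

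The difference is therefore 0 points if missing subjects respond alike, 2.5 to 7.5 points at half the observed rate, and 5 to 15 points if none of them responds.

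**Read as a trend.** Take the extreme case, d = 20% and q = 0. A true all-subject rate fixed at 40% throughout would be shown as 0.40 / 0.80 = 50% at the late visit, a 10-point rise with no change in any subject.

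**Against sampling error.** If all 651 enrol and 20% are missing, about 521 are observed. The 95% half-width at 50% is 1.96 × √(0.5 × 0.5 / 521) = 4.3 points. The difference at d = 20% is 5 points if q = p/2 and 10 points if q = 0, so either would exceed sampling error in the total population.

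**Does stopping for lack of efficacy remove the subject from the denominator?** Not by itself. The interval table in SAP 6.4 sets month 13 to start at "study day 337 if week 48 dose is not received (either missed or IP discontinued prior to week 48"), with matching rules for the earlier months, so off-drug diary data count if they exist. Whether they exist depends on what follow-up the subject agrees to (protocol 8.1). The diary also pauses between months 3 and 5, 6 and 9, and 10 and 12 (protocol 7.2.1.10), so a subject who stops in a pause must resume it to be counted.

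**What the planned tables can recover.** SAP 10.1 gives number and percentage by category, so responder counts will be available. Added over the efficacy groups that share an entry dose, they can be divided by the number dosed at that entry dose in the disposition table. That yields a fixed-denominator rate by entry dose and overall. It does not yield one for each of the six groups, because disposition is not split by parent arm. Nor does any specified table show, visit by visit, how many of the missing had stopped for lack of efficacy.

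**The case against.** The strongest reply has four parts.

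1. **Retention off drug.** A non-responder who stops the product but keeps the diary stays in the denominator, and protocol 12.4 extends data collection to subjects no longer on treatment. This stands. A reader might infer from the stopping reason in protocol 8.3.1 that late-visit efficacy *is* inflated. The documents do not support that: they give neither d nor q, months also go missing for reasons unrelated to response, and the bias is zero if q = p.
2. **Attrition is reported.** A reader might also infer that nothing is planned to examine withdrawal. That is wrong: SAP 9.4 and 10.2 provide for timing, reasons and disposition. But these describe who left. They do not re-estimate the responder rate, and they are not laid out by efficacy group and visit.
3. **The efficacy-set restriction does no harm here.** This stands for the planned tables. A subject with no post-baseline month contributes no value at any visit, so excluding that subject changes no observed-case rate. It matters only once a fixed denominator is used.
4. **Limited consequence.** The study is open-label, its primary endpoint is adverse-event incidence, and efficacy is descriptive with no test or stopping rule attached. This stands, and it limits the importance of the point.

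**Conclusion.** The point holds in a limited form. The responder rate is observed-case at every visit, and no missing-data sensitivity analysis of efficacy is pre-specified. Upward bias at late visits is possible, not established: it requires that subjects without a value respond less often than those observed, for example because those who stop for lack of efficacy also leave the diary.

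On the assumed 50% observed and 10% to 30% missing, the overstatement runs from nothing to 15 points. The upper end is the bound at which every missing subject is a non-responder; it is not a corrected estimate. The planned tables allow a rough check overall and by entry dose, but not within the six groups in which efficacy is reported. This is a cheap improvement to a secondary, descriptive analysis and not a flaw that threatens the study's primary purpose.

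**What to change.** Keep the observed-case table as the primary summary. Add to SAP 10.5 one sensitivity table of the 50% responder rate:

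- at months 1, 2, 3, 6, 10 and 13;
- by the same six parent-arm and first-dose groups, and in total;
- with all dosed subjects (the full analysis set) as the fixed denominator, and missing values counted as non-response;
- labelled as a conservative lower bound;
- with the number observed and the cumulative number discontinued for lack of efficacy printed at each visit.

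The cost is one extra table from data already collected, and the downside is that its estimate is conservative. Using the full analysis set also matches what protocol 10.4.1 says about efficacy. The table covers the responder rate only; mean changes would still rest on observed cases. The pointer in SAP 9.3 can be corrected from 9.3.2 to 9.3.3 in the same edit.

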9.4 Detection of Bias

As an open-label extension study, the potential bias introduced by selecting subjects, allocating treatment groups and assessing endpoints is minimal. However, it is recognized that the data of study 20130255 may suffer from a selection bias associated with dropout from the parent study 20120295. Other factors that may bias the results of the study include:

- important protocol deviations
- investigational product dosing non-compliance
- the timing of and reasons for early withdrawal from treatment and from study in 20130255

The incidence of these factors may be assessed. Important protocol deviations likely to impact the analysis and interpretation of the efficacy endpoints will be listed and/or tabulated in the clinical study report (CSR). If necessary, the incidence of other factors will be tabulated.

The timing of and reasons for early withdrawal from treatment and from study will be tabulated and/or listed. Ad-hoc analysis on time to early withdrawal from treatment and

from study may be performed according to the actual treatment received in the parent study 20120295 or the reasons of early withdrawal.

9.5 Outliers

Histograms may be examined to identify outliers in any of the continuous variables used in the analyses. Unexpected or unexplained values in categorical data may be identified by utilizing frequency tables.

Outliers due to data entry errors will be corrected by the study team before final database lock. The validity of any questionable values or outliers will be confirmed. Outliers or any questionable values with confirmed validity will be included in the analyses. However, ad-hoc sensitivity analyses may be conducted to evaluate the influence of extreme values in the data.

9.6 Distributional Characteristics

Not applicable

9.7 Validation of Statistical Analyses

Programs will be developed and maintained, and output will be verified in accordance with current risk-based quality control procedures.

Tables, figures, and listings will be produced with validated standard macro programs where standard macros can produce the specified outputs.

The production environment for statistical analyses consists of Amgen-supported versions of statistical analysis software; for example, the **SAS System Version 9.4 or later and R**.

For the exposure–response analysis, refer to the E-R SSAP for the software used.

10. Statistical Methods of Analysis

10.1 General Principles

The final analysis for the entire study including open-label treatment phase and safety follow-up phase will be performed at the end of study.

All subjects who have enrolled and received at least one dose of AMG 334 in the study will be included in the data analysis.

For the purpose of secondary and exploratory efficacy endpoints in the 20130255 OLE study, the primary baseline is the 20120295 parent study baseline **(from the first day subject used eDiary in baseline at week -4 study visit through the day prior to**

study day 1). However, change from the parent study month 3 data may also be evaluated.

Efficacy endpoints will be summarized based on their randomized treatment group assignment in the parent study 20120295 **and the first dose received in the 20130255 OLE study.**

Summary descriptive statistics by each treatment group will be tabulated at each visit. For continuous endpoints number of observations, mean, median, standard deviation, first and third quartiles, minimum and maximum, and a two-sided 95% confidence intervals of the mean (except for safety laboratory analyses) will be included for descriptive statistics. For categorical and ordinal endpoints, the summaries will contain the number and percentage of subjects falling into each category.

No formal statistical tests will be performed. Missing values for safety endpoints will not be imputed.

The full analysis set will be utilized to summarize subject disposition of all enrolled subjects, demographic data, and baseline disease characteristics. The efficacy analysis set will be utilized to analyze efficacy endpoints. The SAS will be used to analyze safety endpoints, **which is the same as the FAS. The PRO analysis set will be used for the PRO substudy (ie evaluation of MPFID).**

10.2 Subject Accountability

The disposition of all enrolled subjects will be tabulated by the treatment group allocated in 20130255 OLE study, **based on the dose into which they entered the study**, including the number of subjects enrolled, who receive the open-label treatment phase IP, successfully completed open-label treatment phase IP administration and completed study. The disposition tables will also include the number of subjects who withdrew from the IP and their reasons for withdrawal.

A footnote on the subject disposition tables will include dates first and last subjects enrolled, the date of study completion (eg, last subject completed the safety follow-up visit or drop out from the study) and corresponding data cutoff date.

10.3 Important Protocol Deviations

Important Protocol Deviations (IPDs) categories are defined by the study team before the first subject's visit and updated during the IPD reviews throughout the study prior to database lock. These definitions of IPD categories, sub-category codes, and

descriptions will be used during the course of the study. Eligibility deviations are defined in the protocol.

10.4 Demographic and Baseline Characteristics

Subject demographic and baseline characteristics will be summarized using descriptive statistics by treatment group into which they entered the 20130255 OLE study and overall using the FAS. If multiple races have been reported for a subject, the subject will be categorized as multiple race.

The following demographic and baseline characteristics will be summarized:

- sex
- ethnicity
- race
- age
- age group
- height (cm)
- **Ever used prophylactic medication topiramate (yes vs. no)**
- **Ever used onabotulinum toxin (yes vs. no)**
- targeted neurological disease diagnosis at 20120295 baseline
- migraine acute headache medications used during 20120295 baseline phase (none, any acute medication)
- prior treatment with migraine prophylactic medication (never failed, failed ≥ 1 , failed ≥ 2 medication classes)
- **prior migraine prophylactic medication (yes vs. no)**
- **prior migraine prophylactic treatment failure (yes vs. no)**
- age at onset of migraine
- disease duration of migraine with or without aura
- class of migraine prophylactic treatments (divalproex sodium, sodium valproate, topiramate, beta blockers, tricyclic antidepressants, flunarizine or verapamil, serotonin-norepinephrine reuptake inhibitors, botulinum toxin, lisinopril or candesartan and other) used and without therapeutic response prior to entry into screening
- **discontinuation reason of prior prophylactic medications**
- region (North America vs. others)
- medication overuse (yes vs. no)

The following 20130255 OLE study demographic, baseline characteristics and monthly endpoints during 20120295 baseline phase and during 20120295 month 3 will be summarized:

- weight (kg)
- body mass index (BMI, kg/m²) - using data from 20120295 baseline phase only
- acute migraine-specific medications used:
 - a. triptans
 - b. ergot-derivatives
- monthly migraine days
- monthly migraine attacks
- monthly headache days
- monthly acute migraine-specific medication use (days)
- monthly acute medication use (days)
- monthly headache days with moderate or severe pain intensity
- monthly average severity of migraine pain
- monthly average severity of migraine related symptoms

